All endpoints will be summarized with descriptive statistics including number of subjects (n), number and percent of subjects with missing data, arithmetic means and standard deviations (mean and SD), median, minimum and maximum, for log normally distributed endpoints geometric mean, geometric coefficient of variation (CV) will also be presented (note: categorical variables will be summarized by frequency statistics [number and percentage]). All analyses and summaries will be performed separately for fixed puffing regimen and *ad libitum* use, with the exception of AEs. In addition, PK, PD, and safety variables will be analyzed as follows:

Pharmacokinetic Analysis:

Nicotine plasma PK parameters will be determined from the plasma concentration-time profiles for all evaluable subjects according to conventional Non-Compartmental Analysis (NCA) methods. Actual sampling times, rather than scheduled sampling times, will be used in all computations involving sampling times. For both, the fixed puffing regimen and the *ad libitum* use, background-corrected nicotine plasma concentrations will be used for the estimation of plasma PK parameters by NCA.

Plasma PK parameters will be summarized using descriptive statistics by study product (e.g., subject's own product or P4M3 variant), as appropriate.

For the 60-minute *ad libitum* uses, an analysis of variance (ANOVA) will be conducted on logarithmically transformed cC_{peak} , $cC_{average}$, and $cAUC_{(0-4h)}$, as applicable. The model will be adjusted for sex and cC_{trough} value with product use as a fixed effect and subjects as a random effect. Wilcoxon signed-rank test will be used to compare t_{peak} between the test (P4M3 variant) and reference (subject's own) products.

For the fixed puffing regimens, the ratio of geometric mean nicotine exposure normalized $cAUC_{(0-4h)}$ and cC_{max} for each P4M3 variant in reference to the subject's own e-cigarette will be presented with associated 90% confidence intervals (CIs). The theoretical nicotine exposure, as appropriate, will be used for the purposes of parameter normalization.

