**LIST OF ABBREVIATIONS AND EXPLANATION OF TERMS****Abbreviations**

Adapted mCEQ	Adapted version of the modified Cigarette Evaluation Questionnaire
AE(s)	Adverse event(s)
ALT	Alanine transaminase
ANCOVA	Analysis of covariance
ANOVA	Analysis of variance
AST	Aspartate transaminase
ATS	American Thoracic Society
AUC	Area under the concentration time curve
AUC _(0-4h)	Area under the concentration-time curve from T0 to 4 hours
BMI	Body mass index
cAUC _(0-4h)	Background-corrected area under the concentration-time curve that is above the corrected baseline from T0 to 4 hours for the fixed puffing regimen
cAUC _{b(0-4h)}	Background-corrected area under the concentration-time curve that is above the corrected baseline from T0 to 4 hours for the ad libitum use
CC(s)	Conventional cigarette(s)
cC _{average}	Adjusted average of plasma nicotine concentrations during ad libitum use
cC _{max}	Adjusted maximum concentration
cC _{peak}	Adjusted highest plasma concentration during ad libitum use
CD	Compact disc
CI	Confidence interval
CIOMS	The Council for International Organizations of Medical Sciences
C _{average}	Average of plasma concentrations during ad libitum use
C _{max}	Maximum concentration
C _{peak}	Highest plasma concentration during ad libitum use
C _{trough}	Lowest plasma concentration after T0 during ad libitum use
CO	Carbon monoxide
CORESTA	Cooperation Centre for Scientific Research Relative to Tobacco
CRF	Case report form
CRO	Contract Research Organization
CSR	Clinical Study Report

CTCAE	Common Terminology Criteria for Adverse Events and Common Toxicity Criteria
CTMS	Clinical Trial Management System
CV (%)	Coefficient of variation (%)
CV (documentation)	Curriculum vitae
CYP2A6	Cytochrome P450 2A6
DVD	Digital video disc
e-cigarette	Electronic cigarette
ECG	Electrocardiogram
EOS	End of Study
EU	European Union
FDA	US Food and Drug Administration
FEV ₁	Forced expiratory volume in 1 second
FSH	Follicle-stimulating hormone
FU	Follow-up
FVC	Forced vital capacity
GCP	Good Clinical Practice
HIV	Human immunodeficiency virus
HPHC	Harmful and Potentially Harmful Constituents
HPT	Human puffing topography
IB	Investigator's Brochure
ICF	Informed consent form
ICH	International Council for Harmonisation
IP	Investigational Product
IRB	Institutional Review Board
ISO	International Organization for Standardization
IU	International units
LA	Lactic acid
LLN	Lower limit of the normal range
LLOQ	Lower limit of quantification

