2.2 Purpose of the Study

The goal of the study will be to evaluate the nicotine concentration profiles and derived PK parameters, subjective and behavioral effects, and puffing topography parameters of P4M3 with four liquids of various nicotine concentrations with and without lactic acid (ranging from 1.7% to 4%) in experienced e-cigarette users following a single-use experience with fixed puffing and after *ad libitum* use of P4M3. Four (4) variants of P4M3 with incremental nicotine concentrations ranging from 1.7% (with and without lactic acid) to 4% (with lactic acid) will be evaluated together with subjects' own e-cigarettes to evaluate the relationship between the e-liquid composition (nicotine concentrations and presence of lactic acid) and the amount of nicotine absorbed, the speed of absorption, and the puffing topography. Furthermore, the associations between the PK parameters and human puffing topography parameters following a fixed puffing and *ad libitum* use will be evaluated. Additionally, subjective effects and related behavior will be assessed by the means of questionnaires, to provide further insights on product acceptance. Ultimately, the goal of this study is to select the variant(s) that result(s) in nicotine absorption close to that observed with subjects' own e-cigarettes.

Safety will also be assessed throughout the study.

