3 STUDY OBJECTIVES AND ENDPOINTS

3.1 Primary Objective and Endpoints

Primary Objective and Endpoints

1. To evaluate the plasma concentration-time profile of nicotine and derived PK parameters of the P4M3 variants with subjects' own e-cigarette from the 60 minutes *ad libitum* use.

Endpoints:

- Total and background-corrected plasma nicotine concentration versus time profiles
- Background-corrected peak plasma nicotine concentration [cC_{peak}]
- Time to peak plasma nicotine concentration [t_{peak}]
- Background-corrected trough plasma nicotine concentration [cC_{trough}]
- Background-corrected average of plasma nicotine concentration between 0 to 1 hour [cC_{average}]
- Background-corrected area under the concentration-time curve that is above the corrected baseline from the start of product use to 4 hours [$cAUC_{b(0-4h)}$]

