4.2 Rationale for Study Design

The goal of the study will be to select the P4M3 variant(s) that result(s) in nicotine absorption close to that observed with subjects' own e-cigarettes. The nicotine plasma concentration profiles and derived PK parameters, subjective and behavioral effects, and HPT parameters of P4M3 variants and subjects' own e-cigarettes will be evaluated. The concentrations of nicotine in some of the P4M3 variants tested in this study are already available on the market and exposure of the IPs will be to experienced e-cigarette users aged 21 - 65 years (inclusive) following a single-use experience with fixed puffing in the morning and after *ad libitum* use of P4M3 in the afternoon across 4 days. Subjects with a history of e-cigarette use were chosen for this study based on data from previous studies indicating that having previous experience using such products may impact nicotine exposure and puffing topography (Farsalinos 2013, 2015; Spindle 2015). Further, the use of fixed and *ad libitum* puffing regimens by experienced consumers is expected to provide insight into nicotine delivery by the products that is possible under consistent use conditions across subjects (fixed puffing regimen) as well as a means to assess the products' ability to meet a consumers needs during short-term "real-life" use conditions (*ad libitum* regimen).

Plasma nicotine presents a biphasic profile, with a typical rapid initial disposition half-life ($t_{1/2\alpha}$) of 1.35 hours, followed by a slower terminal elimination half-life ($t_{1/2z}$) of 17 hours (Marchand et al, 2017). To ensure a full nicotine washout between each product use, a separation of 3 days would be required ($\sim 5 \times$ elimination $t_{1/2z}$). Due to the impracticality of undergoing long periods of abstinence for smokers, shorter washout periods have been selected. To minimize the potential bias in the nicotine plasma PK parameters for the fixed puffing regimens, background-concentration correction will be applied to adjust for carry-over effects. The simplest approach by which this can be achieved requires a) a minimum washout-out period of 10 hours prior to each fixed puffing regimen session (this ensures that subjects have entered the terminal elimination phase of nicotine) and b) the estimation of $t_{1/2z}$ (or the terminal elimination rate constant λ_z) on Day 5 for each subject.

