12.1.1 Definitions for Statistical Data Analysis

Unless otherwise stated, for the purposes of statistical analyses, baseline is defined as the last available time point prior to T0 on Day -1.

Nicotine exposure parameters will be derived from plasma nicotine versus time data by NCA using Phoenix WinNonlin, Version 7.0 or higher. C_{max}, AUCs, and related PK parameters, as appropriate, will also be calculated. To minimize the potential bias in the nicotine plasma PK parameters for the fixed puffing regimens, background-concentration correction will be applied to the concentration data and derived PK parameters to adjust for carry-over effects. For nicotine exposure parameters, baseline (C₀) will be defined as the concentration immediately prior to T0 for each session. The baseline correction will be implemented by calculating the nicotine exposure parameters using adjusted concentration values as described below:

The nicotine terminal elimination rate constant λ_z (and $t_{1/2z}$) will be estimated from the Day 5 PK samples (or early termination samples, if available) using a linear regression on the log concentration the pre-T0 time points. The regression analysis should contain data from at least 3 different time points in the terminal phase (including the last quantifiable concentration but excluding the concentration at t_{max}), consistent with the assessment of a straight line on the log-transformed scale. The nicotine plasma background-corrected PK parameters will be derived by performing the NCA on the corrected concentrations.

For the purposes of background-correction of the plasma concentrations post-baseline the following formula will be applied: $cC_t = C_t - C_0 * e^{-\lambda_z t}$. Where, C_t is the corrected concentration at each time point, C_0 is the pre-use baseline concentration, λ_z is the Day 5 (or early termination, if available) terminal elimination rate constant and t is the actual time.

If plasma concentrations cannot be background-corrected in a sufficient number of subjects e.g., in the event that the λ_z (or $t_{1/2z}$) cannot be estimated, modelling approaches may be applied including conventional compartmental analyses. The total (untransformed) PK parameters will be reported and used for statistical analyses instead in case both correction methods are unsuccessful. If warranted, nonlinear mixed-effect modeling using nicotine pooled data across studies may also be used.

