12.5.2 Statistical Analysis

Endpoints for *ad libitum* use will be summarized as described in [Section 12.1.2](#).

Nicotine PK parameters will be derived from plasma nicotine versus time data using non-compartmental analysis. Plasma PK parameters will be summarized using descriptive statistics by product type (e.g., subjects' own e-cigarette or P4M3 variant), as appropriate.

For the 60-minute *ad libitum* uses, an ANOVA will be conducted on logarithmically transformed cC_{peak} , cC_{average} , and $cAUCb_{(0-4h)}$, as applicable. The model will be adjusted for sex and cC_{trough} value with product use as a fixed effect and subjects as a random effect. Wilcoxon signed-rank test will be used to compare t_{peak} between the test (P4M3 variant) and reference (subject's own) products.

Data and information contained in this document are considered to constitute trade secrets and confidential commercial information, and the legal protections provided to such trade secrets and confidential information are hereby claimed under the applicable provisions of US law. No part of this document may be publicly disclosed without the written consent of PMI.

The relationship between nicotine concentrations (with lactic acid only) and the nicotine PK parameters will be investigated graphically on an exploratory basis.

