12.6.2 Statistical Analysis

Nicotine plasma PK parameters will be determined from the plasma concentration-time profiles for all evaluable subjects according to conventional NCA methods. Actual sampling times, rather than scheduled sampling times, will be used in all computations involving sampling times. For the fixed puffing regimen, background-corrected nicotine plasma concentrations will be used for the estimation of plasma PK parameters by NCA. Plasma PK parameters will be summarized using descriptive statistics by study product (i.e., subjects' own e-cigarette or P4M3 variant), as appropriate.

For the fixed puffing regimens, the ratio of geometric mean nicotine exposure normalized $cAUC_{(0-4h)}$ and cC_{\max} for each P4M3 variant in reference the subject's own e-cigarette will be presented with associated 90% CIs. The theoretical nicotine exposure, as appropriate, will be used for the purposes of parameter normalization.

In order to evaluate the PK parameters of the P4M3 variants with subjects' own e-cigarette, an ANOVA will be conducted on logarithmically transformed $cAUC_{(0-4h)}$, cC_{average} , and cC_{\max} , as applicable. The model will include sex and product use as fixed effects and subjects as a random

Data and information contained in this document are considered to constitute trade secrets and confidential commercial information, and the legal protections provided to such trade secrets and confidential information are hereby claimed under the applicable provisions of US law. No part of this document may be publicly disclosed without the written consent of PMI.

effect. For each P4M3 variant, the geometric LSM P4M3 variant:e-cigarette ratios will be presented with 90% CIs. The dose-proportionality of the e-liquid concentrations (with lactic acid only) versus nicotine exposure PK parameters will be investigated graphically on an exploratory basis.

In addition, the impact of the lactic acid will be evaluated for the PK parameters, using an ANOVA on logarithmically transformed $cAUC_{(0-4h)}$ and cC_{max} , adjusting for sex, with sequence, subject nested within sequence, period, and product as fixed effects. The geometric LSM P4M3-1.7%LA:P4M3-1.7% ratios will be presented with 90% CIs. Wilcoxon signed-rank test will be used to compare t_{max} between the study products.

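### The primary ad libitum model adjusts for cC_trough, itself a primary endpoint measured after product use begins, so its product contrasts are not differences in total nicotine exposure

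*Protocol*

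**What the plan says.** Section 12.5.2 plans an ANOVA on the logarithms of cC_peak, cC_average and cAUCb(0-4h) from the 60-minute ad libitum sessions and specifies: "The model will be adjusted for sex and cC_{trough} value with product use as a fixed effect and subjects as a random effect". The synopsis gives the same model, so this is not an isolated slip.

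The list of abbreviations describes C_trough as: "Lowest plasma concentration after T0 during" ad libitum use. Sections 3.1 and 12.5.1 list its background-corrected form, cC_trough, among the primary endpoints.

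The pre-use level is a different quantity. Section 12.1.1 says that the baseline C0 "will be defined as the concentration immediately prior to T0 for each session", and subtracts its decaying remainder from every later concentration.

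For fixed puffing, section 12.6.2 has no such covariate: "The model will include sex and product use as fixed effects and subjects as a random" effect. That paragraph also names cC_average, which section 3.2 marks as ad libitum only.

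The aim in section 4.2 is to "select the P4M3 variant(s) that result(s) in nicotine absorption close to that observed with" the subjects' own e-cigarettes. Section 2.2 relates e-liquid composition to "the amount of nicotine absorbed, the speed of absorption, and the puffing topography".

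**The concern.** A covariate in a product comparison should not be affected by the product. cC_trough is. It is drawn from samples taken while the subject is using the product under test, and it is one of the outcomes that the comparison is meant to describe. Adjusting for it removes whatever part of the exposure difference already shows in the trough. What remains is the difference between products among sessions with the same trough, which mixes amount absorbed with speed of absorption.

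Variant selection is what is at stake. If trough and peak rise together, a weaker or stronger variant will look closer to the own e-cigarette than it is. If a variant delivers the same amount at a different speed, it can look different when total exposure is equal.

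**Working it through.** **Can cC_trough be read as a baseline?** No. The correction in 12.1.1 is cC_t = C_t − C0·exp(−λz·t). At t = 0 this is C0 − C0 = 0, so a corrected pre-use value would be a constant. Section 7.4.1 places the samples during use at 10, 20, 30, 40 and 60 minutes after T0, and the trough comes from these.

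**Plan figures.** The only planning number used here is the sample size in 12.2: 12/(1 − 0.25) = 16, which reproduces. The protocol gives no variances, correlations or expected ratios, so those below are assumptions.

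**Size by formula.** With a covariate in the model,

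adjusted log ratio = total log ratio − β × (product effect on the covariate),

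where β is the slope of log outcome on the covariate within subject and product. With log trough, β = r × SD(peak)/SD(trough). Assume within-subject log SDs of 0.25 (peak) and 0.35 (trough).

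With r = 0.6, β = 0.6 × 0.25/0.35 = 0.429. For a true peak ratio of 0.70 and a trough ratio of 0.60:

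ln 0.70 − 0.429 × ln 0.60 = −0.357 + 0.219 = −0.138, a ratio of 0.87.

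A simulation with 16 subjects, 5 products and 3,000 runs per case gave:

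| Case | Trough ratios | r | True peak ratios | Trough-adjusted |
|---|---|---|---|---|
| Trough moves with peak | 0.60, 0.75, 1.30, 1.70 | 0.6 | 0.70, 0.80, 1.20, 1.50 | 0.87, 0.90, 1.07, 1.19 |
| Same, stronger correlation | same | 0.8 | same | 0.94, 0.94, 1.03, 1.11 |
| Same, negative correlation (e.g. self-titration) | same | −0.4 | same | 0.60, 0.74, 1.29, 1.74 |
| Trough moves the other way | 1.3, 1.2, 0.8, 0.7 | 0.6 | same | 0.62, 0.74, 1.32, 1.74 |
| Equal peaks | 0.60, 0.75, 1.30, 1.70 | 0.6 | all 1.00 | 1.24, 1.13, 0.89, 0.80 |
| Trough unaffected by product | all 1.00 | 0.6 | 0.70, 0.80, 1.20, 1.50 | 0.70, 0.80, 1.20, 1.50 |

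Without the covariate, the true ratios return in every case.

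**Size from a nicotine uptake model.** Intake was simulated in each interval between samples. Disposition was biexponential with the half-lives in section 4.2 (1.35 h and 17 h) and assumed weights of 0.85 and 0.15. Assumed log SDs were 0.4 between subjects, 0.3 between sessions and 0.15 to 0.6 between intervals. Raw cC_trough was the covariate, with 200 trials per scenario.

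- Products differ in amount only: a true cC_peak ratio of 0.60 is estimated at 0.81 when puffing is steady, falling to 0.62 as puffing becomes more variable. A true 1.20 becomes 1.03 to 1.18.
- Same amount, faster uptake: cAUCb(0-4h) ratios of 1.00 to 1.02 become 0.72 to 0.86. For the fastest profile, cC_average of 1.26 to 1.27 becomes 0.88 to 0.89, crossing 1.
- Same amount, slower uptake: cAUCb(0-4h) ratios of 0.99 to 1.00 become 1.26 to 1.50.
- Amount 1.2 with slower uptake: 1.18 becomes 1.46. Amount 0.6 with faster uptake: 0.61 stays 0.61.

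The trough was the 10-minute sample in 98% to 100% of sessions, because intake was assumed in every interval. In that setting the model conditions on early uptake.

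The protocol does not say whether the trough enters raw or logged. Similar runs with log trough moved a true 0.60 to values from 0.62 to 0.92.

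**The case against.** - **The total ratios are already planned output.** Sections 12.1.2 and 12.5.2 call for geometric means by product. With complete data, their ratios equal the product ratios from the model without trough. This stands. The descriptive means do not, however, supply a model-based interval, and section 12.2 allows up to 25% of subjects to have an incomplete period, where the two no longer coincide.
- **Little hangs on it formally.** There is no hypothesis, margin or selection rule, and 12.5.2, unlike 12.6.2, does not say that ratios with intervals will be reported. This also stands: the damage is to estimates and their reading, not to type I error.
- **The trough may be meant as a session reference level.** Section 3.2 uses cC_peak − cC_trough as an endpoint. No rationale carries this over to the ANOVA, and using the difference as an endpoint treats the trough as part of the response.
- **Section 12.6.2 gives cC_average a model without trough.** That paragraph concerns fixed puffing, so the entry may be a stray label. Either way, it offers no alternative for ad libitum cC_peak or cAUCb(0-4h).
- **The magnitudes are assumed.** True, and with highly variable puffing the amount-only bias is trivial (0.62 against 0.60). The existence of the bias does not depend on these figures.

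**Conclusion.** The concern holds, and the model should be changed before analysis. It is the only model stated for ad libitum cC_peak and cAUCb(0-4h), and it answers a different question from the one in section 4.2. Its contrast equals the total exposure difference only if trough is unaffected by product or has no within-product relation to the outcome. The protocol gives no reason to expect either, with variants running from 1.7% to 4% nicotine.

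Bias toward a ratio of 1 is the most plausible direction, since peak, average and trough usually rise together, and it would flatter variants that are not close to the own product. That direction is not assured: under other assumptions the bias is negligible or away from 1. All sizes above rest on assumed variances, correlations and intake profiles.

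**What to change.** 1. In 12.5.2 and the synopsis, delete cC_trough from the ad libitum model. Fit log cC_peak, log cC_average and log cAUCb(0-4h) on product and sex, with subject as a random effect. Keep cC_trough as an outcome only.
2. Reconcile 12.5.2 with 12.6.2 so that cC_average has one model.
3. State in 12.6.2.1 and the synopsis that the VAS craving AUC model does not include cC_trough. Both now refer to the PK model without saying which one. This is a secondary clarification.
4. Do not substitute C0 in the primary model as though it were free of product exposure. Under 6.3.3 the afternoon session follows morning use of the same variant. With the 17 h half-life in 4.2, exp(−ln 2 × 10/17) = 0.665, so about 67% of the terminal component remains after 10 hours. The correction in 12.1.1 already addresses carry-over. C0 belongs at most in a sensitivity analysis.

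The cost is one sentence in each of 12.5.2 and the synopsis, plus the clarifications in items 2 and 3. No new data are needed and the sample size stays at 16. Estimates may move in either direction.

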3.3 Study Hypothesis

There are no statistical hypotheses to be tested.

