12.1.2 Descriptive Statistics

All endpoints will be summarized with descriptive statistics including number of subjects (n), number and percent of subjects with missing data, arithmetic means and standard deviations (mean and SD), median, minimum and maximum. For log normally distributed endpoints geometric mean, geometric CV will also be presented (note: categorical variables will be summarized by frequency statistics [number and percentage]). For endpoints relating to sampling times (e.g. t_{max}) only median and range will be presented. All analyses and summaries will be performed separately for fixed puffing and *ad libitum* use, with the exception of AEs.

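### t_peak, a primary endpoint, is compared between products only by a signed-rank test, with no paired difference or interval, and the t_max comparison with the own e-cigarette is not clearly planned

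*Protocol*

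**What the plan says.** All references are to the Protocol.

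- **Status of the endpoint.** Section 3.1 lists t_peak among the primary endpoints. Section 3.2 lists t_max as a secondary one.
- **Purpose.** Sections 2.2 and 4.2 give the goal as choosing variants whose nicotine absorption is near that of the own e-cigarette. Section 2.2 names speed of absorption as one of the things studied.
- **Hypotheses.** Section 3.3: "There are no statistical hypotheses to be tested".
- **Analysis of t_peak.** Section 12.5.2: a "Wilcoxon signed-rank test will be used to compare" t_peak of each P4M3 variant with that of the reference, the own e-cigarette. It also says "Plasma PK parameters will be summarized using descriptive statistics by product type".
- **Analysis of t_max.** Section 12.6.2: "Wilcoxon signed-rank test will be used to compare t_{max} between the study products". The sentence closes the paragraph on lactic acid, which compares P4M3-1.7%LA with P4M3-1.7%.
- **Summaries.** Section 12.1.2 says that for sampling-time endpoints "only median and range will be presented".
- **Times used.** Section 12.6.2: "Actual sampling times, rather than scheduled sampling times, will be used in all computations involving sampling times".
- **Contrast.** For fixed-puffing exposure, 12.6.2 plans geometric mean ratios of each variant to the own e-cigarette with 90% CIs.

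**The concern.** Closeness is a question about the size of a difference and how well it is known. A signed-rank test answers another question: whether the data are incompatible with no shift. In a small study with no stated hypothesis, alpha, margin or power, a large p-value mainly reflects the sample size. If it is the only between-product result for t_peak, it can be taken to mean that a variant delivers nicotine as fast as the own product. Medians by product do not fill the gap: a difference of two medians ignores the pairing, and a range is not a measure of precision.

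For t_max the difficulty comes one step earlier. From its place in the text, the test may cover only the two 1.7% variants, or all products. If only the former, speed under fixed puffing is never compared with the reference product.

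**Working it through.** **The plan's own figure.** Section 12.2 targets 12 subjects and allows for up to 25% with incomplete data: 12 / (1 − 0.25) = 16. This reproduces the 16 to be randomized. No power or effect size is given for t_peak or t_max.

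**What the same data can give.** For n paired differences there are n(n + 1)/2 Walsh averages. Their median is the Hodges-Lehmann estimate, and the exact signed-rank distribution gives the interval.
- n = 12: 12 × 13 / 2 = 78 averages; the 18th smallest to the 18th largest has 90.8% coverage.
- n = 16: 16 × 17 / 2 = 136 averages; the 36th smallest to the 36th largest has 90.7% coverage.

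**Precision and power under assumptions.** Section 7.4.1 draws blood at 10 ± 1, 20 ± 2, 30 ± 2, 40 ± 5 and 60 ± 5 minutes during ad libitum use. The documents give no distribution of t_peak, so three were assumed over these five draws:
- late (5, 10, 15, 20, 50%): mean 0.5 + 2 + 4.5 + 8 + 30 = 45 min
- middle (10, 20, 30, 20, 20%): mean 1 + 4 + 9 + 8 + 12 = 34 min
- uniform (20% each): mean 32 min

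Actual times were taken as uniform within the windows. Products were either independent within subject, or half the subjects kept the same draw. There were 2,000 runs per case. Mean full width of the 90% CI, over all pairings examined:

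| | n = 12 | n = 16 |
|---|---|---|
| Independent | 25.0 to 26.5 min | 21.4 to 22.6 min |
| Half keep the same draw | 15.4 to 17.9 min | 12.3 to 15.1 min |

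True mean shifts are 45 − 34 = 11 and 45 − 32 = 13 min if independent, and half that (5.5 and 6.5 min) if half the subjects keep the draw. Rejection rate of a two-sided 5% signed-rank test:

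| | n = 12 | n = 16 |
|---|---|---|
| Shift 5.5 min | 12% | 16% |
| Shift 6.5 min | 15% | 19% |
| Shift 11 min | 28% | 40% |
| Shift 13 min | 33% | 47% |

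Non-significance is thus the more likely result in every one of these cases, although a difference exists.

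**Draw-time windows.** Two sessions that peak at the same nominal draw can differ through the window alone by 2 × 1 = 2 min (10-minute draw), 2 × 2 = 4 min (20 and 30) or 2 × 5 = 10 min (40 and 60). In the assumed cases 20% to 66% of pairs share a nominal draw. Random draw-time error did not inflate the error rate: with equal distributions the test rejected in 3.5% to 5.1% of runs. A systematic 3-minute timing difference between products, with all 12 subjects peaking at the 60-minute draw, led to rejection in 57% of runs.

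Nothing was computed for t_max, whose grid and windows differ.

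**The case against.** **Detail for the SAP.** Section 12.1 leaves full detail to the SAP, which is not at hand, and an estimator to go with a named test often sits there. Section 12.1.2 can also be read as covering descriptive summaries only, without barring a paired estimate. This lowers the weight of the point but does not remove it: the protocol names a test as the comparison for a primary endpoint, and its only statement on what is presented for time endpoints is restrictive.

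**Not unique to t_peak.** Section 12.5.2 names no interval for the ad libitum exposure parameters either. That is true, although those at least come from a model that yields estimates.

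Three stronger readings are tempting, and the documents do not support them.

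- *The trial cannot say how close absorption speed is.* It can. Medians and ranges by product are planned, the concentration-time profiles are themselves a primary endpoint, and the paired data allow the estimate with no change of design.
- *Ties make the test nearly useless.* On nominal times, if 70% of sessions peaked at one hour and the rest spread evenly over five other draws, a pair would be untied with probability 1 − (0.7² + 5 × 0.06²) = 0.492, so 12 × 0.492 = 5.9 pairs would count on average. But the plan uses actual times, on which same-draw pairs are rarely tied, and the 70% is an assumption.
- *Actual times invalidate the test.* Random draw-time error does not. A systematic shift would, and since the own product is always used on Day -1 it would be confounded with product, but nothing in the protocol suggests that one will occur.

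**Conclusion.** The point holds for t_peak: as written, the plan offers a significance test and unpaired medians with ranges, but no paired difference and no precision, in a study whose goal is closeness and which declares no hypotheses. A non-significant p-value from 12 subjects would not show similar speed. The figures of 12% to 33% rejection at n = 12 and interval widths of about 15 to 26 minutes rest on assumed peak-time distributions and within-subject dependence; they show the order of magnitude and are not predictions.

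For t_max the finding is one of wording: a comparison with the own e-cigarette is not clearly planned. The draw-time issue justifies a sensitivity analysis, not a change of the main time scale. The design and the data collected are sound for this purpose, and only the analysis text needs to change.

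**What to change.** 1. In 12.5.2, report for each variant the Hodges-Lehmann median paired difference in t_peak (variant minus own e-cigarette) with a 90% CI, on actual times. Treat any signed-rank p-value as descriptive.
2. In 12.6.2, state which t_max comparisons are made, and report the same estimate with a 90% CI for each variant minus own e-cigarette and for P4M3-1.7%LA minus P4M3-1.7%.
3. Amend 12.1.2 so that time endpoints may carry a paired difference and interval beside median and range.
4. Add a sensitivity analysis on nominal draw times, with a count of subjects whose peak falls earlier, at the same draw, or later than with the comparator. Nominal times should not replace actual times as the main analysis, because they create many ties, for which the exact interval is not built.

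The cost is a short change of protocol and SAP text and a small table. No new data are needed. The drawback is that the intervals will be wide and may not settle the question of closeness, but the report will then show that openly.
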